Lyme disease is the most common vector borne disease in the United States. Although antibiotic therapy is clinically effective in treating the symptoms of Lyme disease for most patients early in the course of disease, a significant number of patients who receive therapy report persistent symptoms. The cause of persistent symptoms after antibiotic therapy for Lyme disease is an area of great controversy. Recent studies have shown that the organism (*Borrelia burgdorferi*) may persist in animals after antibiotic therapy and can be detected by using the natural tick vector (*Ixodes scapularis*) to acquire the organism through feeding (xenodiagnosis). Whether this occurs in humans is unknown. Currently available tests for human Lyme disease do not allow determination of persistent infection after antibiotic therapy.

We performed the first study of the use of *I. scapularis* larva for the xenodiagnosis of *B. burgdorferi* infection in humans. Our pilot study showed that xenodiagnosis was well tolerated with no severe adverse events (AEs). The most common AE was mild itching at the site. In this small pilot study, xenodiagnosis for *B. burgdorferi* was positive in 2 participants and indeterminate in 2 participants. Further studies are needed to determine the sensitivity of xenodiagnosis in evaluating the infection status of Lyme disease patients.

In this proposal, we want to further investigate the utility of xenodiagnosis for identifying persistence of infection with *B. burgdorferi* in treated human Lyme disease. Our objectives include assessing the link between detection of *B. burgdorferi* by xenodiagnosis and persistence of symptoms in patients diagnosed with Lyme disease, within 1 year, post therapy; compare the rate of detection of *B. burgdorferi* by xenodiagnosis after therapy in participants with post-treatment Lyme disease symptoms; identify subject characteristics related to the likelihood of detecting *B. burgdorferi* by xenodiagnosis including: time from infection, time between infection and therapy, time from therapy; and continue to assess the safety of xenodiagnosis in humans.

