2 STUDY OBJECTIVES

1. Objective #1:
Assess the link between detection of *B. burgdorferi* by xenodiagnosis and persistence of symptoms in patients diagnosed with Lyme disease, within 1 year, post therapy.
2. Objective #2:
Compare the rate of detection of *B. burgdorferi* by xenodiagnosis after therapy for Lyme disease in participants with symptoms of post-treatment Lyme disease.
3. Objective #3:
Identify subject characteristics related to the likelihood of detecting *B. burgdorferi* by xenodiagnosis including: time from infection, time between infection and therapy, time from therapy.
4. Objective #4:
Continue to assess the safety of xenodiagnosis in humans.

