3.2 Inclusion Criteria

Criteria for the diagnosis and therapy for Lyme disease can be found at “The clinical assessment, treatment, and prevention of Lyme disease, human granulocytic anaplasmosis, and babesiosis: clinical practice guidelines by the Infectious Diseases Society of America”⁵.

Patients with Lyme disease, post-therapy (N=100)

1. Age 18 or older.
2. Lyme disease diagnosed in the previous 13 months, fulfilling the case definition of confirmed or probable Lyme disease by the US Centers for Disease Control and Prevention (CDC) <https://www.cdc.gov/nndss/conditions/lyme-disease/case-definition/2017/>.
3. Completion of 1 course of antibiotics at least 3 months and up to 12 months between the end of the therapy and the xenodiagnostic procedure.
4. Antibiotic treatment fulfills the Infectious Diseases Society of America guidelines for the recommended therapy for Lyme disease⁵.

Patients with post-Lyme disease complaints at least 12 months from initial treatment (N=40)

1. Age 18 or older.
2. Diagnosed with confirmed or probable Lyme disease fulfilling the case definition of Lyme disease by the CDC <https://www.cdc.gov/nndss/conditions/lyme-disease/case-definition/2017/>.
3. Received recommended antibiotic therapy for Lyme disease⁵ at least 12 months between the end of the initial antibiotic therapy and the xenodiagnostic procedure.
4. Persistent or recurrent symptoms that began or worsened within 6 months of the diagnosis and treatment for Lyme disease.

Acute EM (N=40)

1. Age 18 or older.
2. EM diagnosed by the study physician.
3. Receiving antibiotic therapy for Lyme disease for less than 48 hours.

Lyme Arthritis (N=40)

1. Age 18 or older.
2. Lyme arthritis⁵⁰ and have not received antibiotic therapy for the disease.

Healthy volunteers (N=20)

1. Age 18 or older.
2. No prior history of Lyme disease.
3. Negative whole cell enzyme-linked immunosorbent assay (ELISA) or C6-based antibody test for Lyme disease.

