For the other groups post-Lyme disease syndromes (PLDS), acute EM, and untreated Lyme arthritis, the precision with which the rates can be estimated from the observed data depends on the true underlying response rate and the sample size. Exact Clopper-Pearson 2-sided 95% CIs for the observed positivity rate the different proposed group sizes and a range of numbers of positive individuals are shown in Table 3. Healthy volunteers (negative controls) results will be used for specificity of the testing.

Table 3: Exact 95% Confidence Interval for the Observed Positivity Rate, for Varying Group Size (N) and Observed Numbers of Positive Individuals

# of observed positives samples	N=20	N=40
0	(0.000, 0.161)	(0.000, 0.09)
1	(0.009, 0.236)	(0.004, 0.13)

2	(0.0279, 0.301)	(0.014, 0.165)
5	(0.112, 0.468)	(0.054, 0.261)
10	(0.299, 0.701)	(0.142, 0.402)
15	(0.531, 0.888)	(0.242, 0.529)
20	(0.838, 1)	(0.352, 0.648)

Data will be collected for any positive tests by xenodiagnosis. Because there is no gold standard test among those we will employ, comparative positivity rates between the tests will be determined. Summaries of patient characteristics will be assessed by study group. For categorical variables, the numbers and proportions will be tabulated; for continuous variables, the mean, median, SD, and interquartile range will be reported. Fisher's exact test will be used to examine the association of 2 categorical variables. For continuous variables, t-tests and nonparametric methods, such as the Wilcoxon or Spearman's correlation coefficient, may be used to assess associations between subgroups of patients.

AEs related to xenodiagnosis will be tabulated and summaries with numbers and proportions will be given.

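### Objective 2 names no comparator, and no analysis is specified that sets positivity in treated patients against the healthy volunteers; a low rate could be reported as detection when 20 controls cannot exclude background

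*Combined protocol and SAP*

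**What the plan says.** Objective 2 in section 2 reads: "Compare the rate of detection of *B. burgdorferi* by xenodiagnosis after therapy for Lyme disease in participants with symptoms of post-treatment Lyme disease". The Précis repeats it, again with one population: "compare the rate of detection of *B. burgdorferi* by xenodiagnosis after therapy in participants with post-treatment Lyme disease symptoms".

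Section 7.1 powers one contrast, symptomatic against asymptomatic individuals. For the post-Lyme, acute EM and Lyme arthritis groups it says that "the precision with which the rates can be estimated from the observed data depends on the true underlying response rate and the sample size", and it refers to the one-sample intervals of Table 3. The only stated role of the healthy volunteers is this: "Healthy volunteers (negative controls) results will be used for specificity of the testing". The section also plans Fisher's exact test for pairs of categorical variables, without naming the groups or the outcome, and a comparison of positivity rates between the different tests.

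Section 3.2 sets the sizes: 100 patients post-therapy (Group 1 in Table 1), 40 with post-Lyme complaints at least 12 months after treatment (Group 2) and 20 healthy volunteers (Group 5). Section 7.3 promises a positivity rate in treated patients and the symptom contrast. It does not mention the controls.

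**The concern.** A comparison needs two sides. Objective 2 could mean Group 2 against healthy volunteers, against Group 1, or against asymptomatic patients, and neither section 2 nor section 7.1 says which. As written it cannot be answered, and the comparator could be chosen after the results are seen.

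The choice matters because section 6 (Benefits) treats a positive result as showing that the participant still harbors the organism, and expects a major shift in thinking if persistence is shown. At group level, that reading requires positivity above the test's own false-positive rate. Section 7.1 acknowledges that there is no gold standard among the tests, so the negative controls are the direct evidence on background. A patient interval and a separate specificity figure do not show whether the two rates differ. Phase 1 found few positives (2 positive and 2 indeterminate participants), and background matters most at low rates.

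**Working it through.** **Inputs.** Group 2 N = 40, Group 1 N = 100, healthy volunteers N = 20 (section 3.2). Phase 1 positivity in symptomatic patients 10%; planning rates 5% (asymptomatic) and 30% (symptomatic); alpha 0.05, power 80% (section 7.1). The documents give no healthy-volunteer positivity rate, so 0% to 5% is assumed below. All patients are taken as evaluable.

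**1. The plan's own sample size.** For p1 = 0.05, p2 = 0.30, mean 0.175, two-sided:

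n = [1.96·√(2·0.175·0.825) + 0.842·√(0.05·0.95 + 0.30·0.70)]² / 0.25² = 35.06 per group.

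With continuity correction: n' = (35.06/4)·[1 + √(1 + 4/(35.06·0.25))]² = 42.7, so 43 per group and 86 in total, as printed. All eight cells of Table 2 reproduce this way. The powered contrast is arithmetically sound and does not involve the controls.

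**2. What 0/20 controls can exclude.** Clopper-Pearson upper limit: 1 − 0.025^(1/20) = 0.168. Specificity is therefore supported only down to 1 − 0.168 = 0.832. Table 3 is labelled Clopper-Pearson but prints 0.161, which is the Wilson value: 1.96²/(20 + 1.96²) = 0.161. Either limit exceeds the 10% seen in Phase 1 symptomatic patients and the 5% planning rate for asymptomatics.

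**3. How a low rate would read.** Take 4/40 (10%) in Group 2.
- One-sample exact 95% CI: 2.8% to 23.7%. It excludes zero.
- Fisher against 0/20: with 4 positives among 60 people, the hypergeometric probabilities of 0, 3 and 4 falling among the controls are 0.187, 0.094 and 0.010. The other two outcomes are more probable than the one observed, so p = 0.187 + 0.094 + 0.010 = 0.29.

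**4. Positives needed for two-sided Fisher p ≤ 0.05.**

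| Controls | Group 2 (N = 40) | Group 1 (N = 100) |
|---|---|---|
| 0/20 | 8 (20%), p = 0.043 | 18 (18%), p = 0.041 |
| 1/20 | 11 (27.5%), p = 0.047 | 26 (26%), p = 0.042 |

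**5. Power of that test.** Power is the sum, over all tables with p ≤ 0.05, of the product of the two binomial probabilities. With a control rate of 0%, for 40 v 20, it reduces to P(X ≥ 8) for X binomial(40, p).

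| True patient positivity | 40 v 20, control rate 5% | 40 v 20, control rate 0% |
|---|---|---|
| 10% | 2% | 4% |
| 20% | 26% | 56% |
| 30% | 64% | 94% |

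For 100 v 20 the corresponding ranges are about 1%, 29–73% and 72–99.8%.

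**6. Effect on the powered contrast.** If a share d of a group is truly detected and the false-positive rate is f, observed positivity is d + (1 − d)·f. With the same f in both groups the difference is (d2 − d1)·(1 − f). It is zero when d2 = d1 and shrinks as f rises, for example by a factor of 0.832 at f = 0.168. A shared false-positive rate dilutes a difference and does not create one.

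**The case against.** Four points on the other side have weight.

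- **A test is permitted.** Positivity by study group is a pair of categorical variables, so the Fisher sentence covers it. That stands. A reader might infer that patients will never be tested against controls; the text supports only that no such test is specified.
- **The main analysis is elsewhere.** A reader might infer that Objective 1 is undermined too. It is not, provided the false-positive rate is the same in both symptom groups (step 6).
- **The controls are not the only protection.** Section 4.8 says the organism does not pass from mother tick to larvae, and has larvae from each egg mass and batch tested and positive egg masses discarded. Section 4.9 allows PCR, culture and/or immunofluorescence on recovered ticks. Section 4.7 offers an optional repeat after a positive result, and section 4.10 compares optional biopsies with the tick results. This supports individual positives. It does not replace a control group, because contamination after feeding remains possible and the repeats and biopsies are optional.
- **The imprecision is disclosed.** Table 3 already shows an upper limit of 0.161 for 0/20. That is true, but the plan does not connect it to the patient rates.

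Two further inferences should be resisted. Reaching 8/40 is not a fixed mark of exceeding background, because the count depends on the controls and rises to 11/40 at 1/20. Nor can the 10 Phase 1 healthy volunteers simply be added. Section 1 does not say which groups the positive and indeterminate results came from, and early Phase 1 participants had fewer ticks feed.

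**Conclusion.** The point holds within these limits. Objective 2 lacks a comparator in both places where it is stated, and section 7.1 specifies no analysis of patients against controls. One-sample intervals could present a rate such as 10% as detection when 0/20 controls leave up to 16.8% background possible and the direct comparison gives p = 0.29.

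The gap affects Objective 2 and any group-level statement that treated patients carry the organism. It does not affect the validity of the symptomatic-versus-asymptomatic test.

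Specifying the comparison will not make 20 controls strong. Against 40 patients, power is low at 10% positivity under any control rate considered, and is 64–94% at 30%. These figures rest on the assumed 0–5% control rate, full evaluability, and the controls being free of infection. That last status is presumed from history and serology; the section 3.2 criteria ask for a negative ELISA or C6 test, while the text that follows says both.

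**What to change.** 1. The sponsor names the comparator for Objective 2, in section 2 and in the Précis, before results are known.
2. Section 7.1 adds the difference in positivity between Group 2 and the healthy volunteers, with an exact 95% CI (method named) and Fisher's exact test. The same analysis for Group 1 is labelled secondary, so that the added comparisons have a stated order.
3. Section 7.1 states that 0/20 supports specificity of at least about 83% only, and either recomputes Table 3 by Clopper-Pearson or relabels it as Wilson.
4. The reach is given as a range: 8/40 against 0/20, 11/40 against 1/20, and the power table above with its assumed control rates. No single count is presented as the threshold for exceeding background.
5. Phase 1 volunteers are not pooled with the controls.

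This uses data already to be collected and needs no new participants or procedures. The cost is a few exact analyses and a more modest stated reach for Objective 2.

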7 STUDY ANALYSIS

7.1 Sample Size Justification

This study is powered to detect difference in the positivity rate between symptomatic and asymptomatic individuals. Self-reported symptoms will be characterized using symptom scales, the SF-36v2 questionnaire and fatigue scales. We will use a composite score derived from the measurement to assign symptomatic and asymptomatic status to the participants.⁷⁹

While the majority of the patients with Lyme disease who were treated with antibiotic therapy were negative by xenodiagnosis in our Phase 1 study, the number of patients tested in each group was small and the upper limit of the 95% confidence interval of each proportion is relatively high (up to 46%). Also, an important caveat is that the number of tested xenodiagnostic ticks per participant in general was also small, and the number of engorged ticks that are tested for each individual is an important variable, as the more engorged ticks tested, the larger the probability of detecting a positive. For example, if the true sensitivity for a single engorged tick to detect the bacteria is 1/10 (based on results of the mice studies), then one would need to recover 14 engorged ticks to have 75% sensitivity and 22 fed ticks to have 90% sensitivity.

Based in our very preliminary data, the upper limit of the exact 95% confidence interval for the proportion of positive xenodiagnosis in symptomatic patients (10%) was 0.445. Table 2 shows the sample size needed for 80% power, with a Type I error rate of 0.05, assuming varying assumptions for the true prevalence rates for asymptomatics (p_1) and symptomatics (p_2). For example, with a total sample size of 86 individuals, there would be 80% power to detect a between-group difference in the positivity rate if the true prevalence is 5% or less in the non-symptomatics and at least 30% in the symptomatics, assuming equal numbers between the 2 groups, (43 non-symptomatics and 43 symptomatics).

Table 2: Sample Size Needed for 80% Power with a Type I Error Rate of 0.05, and Varying Assumptions for the True Prevalence Rates for Asymptomatics (p_1) and Symptomatics (p_2)

	$p_2 = 0.40$	$p_2 = 0.30$
$p_1 = 0.05$	54	86
$p_1 = 0.025$	46	68
$p_1 = 0.01$	42	60
$p_1 = 0$	40	56

Assuming a 10 to 20% rate of missing data due to failed screenings, assays or participant drop-out, we plan to recruit up to 100 individuals.

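### Optional gain: Boschloo's test in place of Fisher's for the symptomatic versus asymptomatic comparison keeps the 5% error limit and adds about 2 points of power on average

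*Combined protocol and SAP*

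**What the plan says.** All of this is in Section 7.1 of the combined protocol and SAP.

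- The sizing target: "This study is powered to detect difference in the positivity rate between symptomatic and asymptomatic individuals".
- The operating characteristics: "Table 2 shows the sample size needed for 80% power, with a Type I error rate of 0.05". Sidedness and the sample-size formula are not stated.
- The worked example: "with a total sample size of 86 individuals, there would be 80% power to detect a between-group difference in the positivity rate". The rates behind it are at most 5% for asymptomatic and 30% or more for symptomatic participants. It assumes two groups of 43. The plan allows for 10 to 20% missing data and recruits up to 100.
- How the groups arise: "We will use a composite score derived from the measurement to assign symptomatic and asymptomatic status to the participants". The split is therefore an outcome of the study and is not set by design.
- The test, in the text after Table 3: Fisher's "exact test will be used to examine the association of 2 categorical variables". This is a general rule for categorical pairs. No test is named specifically for Objective 1, and no reason is given for preferring a conditional test.

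**The concern.** Fisher's test conditions on both margins of the 2 x 2 table. Here neither margin is fixed: symptom status comes from a score, and the number of positives is observed. With few positives, few tables are possible once the margins are fixed, so the attainable p-values are widely spaced and the test usually rejects less often than 5% under the null. The plan states its aims as an unconditional type I error of 0.05 and an unconditional power of 80%. On those criteria, unused error rate is unused power.

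This could matter because the margin over 80% may shrink. Missing data of 20% on 100 recruits leaves 80 evaluable, fewer than the 86 in the example. The groups may also be unequal: Section 1 puts persistent symptoms at 12 months in 10 to 40% of treated erythema migrans patients.

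**Working it through.** **Inputs.** From Section 7.1: type I error 0.05; rates 5% and 30%; 43 + 43; 10 to 20% missing from 100. Assumed: two-sided testing, because this reproduces Table 2 and one-sided testing does not.

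**Step 1. Reproduce the plan's 86.** Normal-approximation size per group, with mean rate 0.175 and difference d = 0.25:

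n = [1.960 x sqrt(2 x 0.175 x 0.825) + 0.842 x sqrt(0.05 x 0.95 + 0.30 x 0.70)]^2 / 0.25^2 = (1.053 + 0.427)^2 / 0.0625 = 35.06.

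Continuity correction: n' = (n/4) x [1 + sqrt(1 + 4/(n x d))]^2 = 8.765 x (1 + 1.207)^2 = 42.7, rounded up to 43 per group, 86 in total. The same formula gives all eight Table 2 cells. Without the correction the total is 72; one-sided it is 56 (72 with correction). So the plan's sample size already allows for a conservative test.

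**Step 2. Enumerate both tests.** For group sizes n1 and n2, each pair of positive counts (x, y) has probability Bin(x; n1, p1) x Bin(y; n2, p2). Power is the sum over the rejection region. Type I error is the same sum with p1 = p2 = p, maximised over a fine grid of p. Fisher rejects when its p-value is at most 0.05. Boschloo uses the Fisher p-value as its statistic and raises the cut-off as far as the maximum type I error allows without passing 5%. At 43/43 the cut-off becomes 0.075. Boschloo's region therefore always contains Fisher's.

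**Step 3. Type I error at 43/43.**

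| Common rate | Fisher | Boschloo |
|---|---|---|
| 5% | 0.5% | 1.6% |
| 10% | 1.9% | 3.3% |
| 17.5% (pooled planning rate) | 2.5% | 4.1% |
| 30% | 3.0% | 4.7% |
| maximum over all rates | 3.18% | 4.96% |

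The exactly equal split is close to the worst case for Fisher. Its maximum is 4.1% at 44/42, 4.3% at 50/36 and 4.7% at 52/34. Across the unequal splits checked it is about 3.6% to 4.7%, apart from an extreme 77/9, where it is 3.2%. Boschloo stayed at or below 5% throughout.

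**Step 4. Power for 5% versus 30%** (asymptomatic/symptomatic).

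| Split | Fisher | Boschloo |
|---|---|---|
| 43/43 | 84.4% | 88.7% |
| 44/42 | 89.2% | 89.5% |
| 46/40 | 86.6% | 86.6% |
| 58/28 | 82.7% | 87.2% |
| 60/26 | 81.9% | 85.1% |
| 40/40 | 82.1% | 85.6% |
| 50/30 | 84.8% | 84.9% |
| 60/20 | 78.3% | 82.3% |

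The 60/20 row takes 100 x (1 - 0.20) = 80 evaluable and a symptomatic share of 25%, an assumption inside the 10 to 40% in Section 1. Over 43/43 and the even-numbered splits of 86 from 26/60 to 60/26, the gain runs from about 0 to 4.6 points. That is not a bound: at 77/9 power goes from 53.9% to 59.5%. If each of 86 participants is equally likely to fall in either group, average power is 86.8% for Fisher and 88.8% for Boschloo, a gain of 2.0 points. With 60% or 70% expected asymptomatic, the average gain is about 2.1 or 2.4 points.

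**Step 5. Lower detection rates.** Section 7.1 gives 75% sensitivity with 14 engorged ticks. Treating 5% and 30% as true infection rates and assuming no false positives, the observed rates are 0.75 x 5% = 3.75% and 0.75 x 30% = 22.5%. At 43/43 power goes from 67.2% to 73.6%; over random splits of 86 the average gain is about 3 points.

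**Step 6. What it can change.** 0/43 versus 5/43 gives p = 0.055 by Fisher and 0.040 by Boschloo; 1/43 versus 7/43 gives 0.058 and 0.040.

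**The case against.** The strongest reply is that nothing is broken. Fisher's test controls the error rate, is familiar, and suits a contested question. The continuity-corrected sample size already pays for its conservatism, and the stated power is met at 43/43 and 40/40. That stands, and it makes this an optional improvement.

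Two stronger readings are tempting. A reader might infer that Fisher's test generally spends only about 3% of the 5%. That holds at exactly equal groups; one participant moved across (44/42) raises the maximum to 4.1%, and the score makes an exact 43/43 split unlikely. Part of the 43/43 gap is discreteness at one point: Fisher at 44/42 (89.2%) beats Boschloo at 43/43 (88.7%). A reader might also infer a large gain when positives are very rare, for instance 0% versus the 10% seen in symptomatic Phase 1 patients. There the gain depends on the split: both tests give 59.7% at 45/41 and 49.1% at 50/36. Nor is this a Table 2 scenario, since that table uses 30% and 40% for symptomatic participants.

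Some statisticians prefer conditional inference on principle. The plan, however, sets only unconditional error and power targets and gives no argument for conditioning, so this does not settle the matter for Fisher. Finally, the named test is a general rule; applying it to Objective 1 is an inference, though a natural one.

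**Conclusion.** A cheap improvement in efficiency, of low importance. On the plan's own criteria Boschloo's test is at least as good as Fisher's in every split checked: the error rate stays within 5% and power is never lower. The expected benefit at the planning rates is about 2 points, and about 3 points if rates are scaled down by 75% sensitivity. It makes a practical difference mainly where the evaluable number is low and the split uneven, as at 60/20, where it restores the stated 80%. The documents do not support saying that the trial is underpowered because of Fisher's test or that the planned analysis is invalid.

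The result rests on two-sided testing, independent binomial counts given the observed group sizes, and use of the general Fisher rule for Objective 1. One-sided at 0.05 the pattern at 43/43 is the same: maximum error 3.3% against 4.8%, power 90.9% against 93.0%.

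**What to change.** Add one sentence to Section 7.1 before any results are seen: the Objective 1 comparison of positivity between symptomatic and asymptomatic participants will use Boschloo's unconditional exact test at two-sided 0.05. State the two-sided definition, either the two-sided Fisher p-value as the statistic or two one-sided tests at 0.025; at 43/43 both give 4.96% maximum error and 88.7% power. Report Fisher's p-value as a sensitivity result only, and say that Boschloo's decides, because the two can fall on opposite sides of 0.05 and choosing afterwards would forfeit error control.

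An uncorrected chi-square test is not a substitute: its maximum type I error at 43/43 is 6.0%.

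The cost is one sentence and a less familiar test that some colleagues will question. No extra participants, procedures or data are needed.
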